## 6.3.1 Primary Efficacy Endpoint

Subjects are instructed to report headache occurrence, headache pain features and associated symptoms, aura occurrence, and medication used to treat headache or aura in the eDiary headache report every day in the OP and DBT Phase.

Migraine days per month are assessed as "migraine days per 4 weeks" to correspond with the 4-week visit schedule. Migraine days per month are based on 4-week intervals, and are prorated to account for missing migraine reports.

See Section 9.2.2 for the definition of eDiary efficacy data days, and Section 9.2.5 for the definition of migraine days.

The number of migraine days per month in the DBT Phase is examined relative to the number of migraine days per month in the OP for the migraine analysis set, i.e., subjects with  $\geq 14$  days of eDiary efficacy data (not necessarily consecutive) in both the OP analysis period and  $\geq 1$  month (i.e., 4-week interval) in the on-DBT efficacy analysis period.

Months in the DBT Phase are defined as follows:

- Month 1:  $\leq$  4 weeks; study days 1 to 28
- Month 2: > 4 to  $\le 8$  weeks; study days 29 to 56
- Month 3: > 8 to  $\le 12$  weeks; study days 57 to 84.

Analyses are based on eDiary efficacy data dates in the OP and on-DBT efficacy analysis periods.

The number of migraine days per month is prorated to 28 days and derived as follows:

• OP: 28 × (total number of migraine days in the OP analysis period)/(total number of eDiary efficacy data days in the OP analysis period). Subjects must have ≥ 14 days of eDiary efficacy data (not necessarily consecutive) in the OP to be evaluable.

- Month (i.e., 4-week interval) in the on-DBT efficacy analysis period: 28 × (total number of migraine days in the month)/(total number of eDiary efficacy data days in the month).
   Subjects must have ≥ 14 days of eDiary efficacy data (not necessarily consecutive) in the specified month to be evaluable.
- Overall DBT: 28 × (total number of migraine days through Month 3 in the on-DBT efficacy analysis period)/(total number of eDiary efficacy data days through Month 3 in the on-DBT efficacy analysis period).

# 6.3.1.1 Missing Efficacy Data

The frequency table of missing efficacy data in the OP and DBT Phase is provided for the full analysis set, and displays the following categories:

- Included in the migraine analysis set:  $\geq$  14 days of eDiary efficacy data (not necessarily consecutive) in both the OP and  $\geq$  1 month (i.e., 4-week interval) of the DBT Phase
  - Month 1:  $\leq$  4 weeks \*
  - Month 2: > 4 to  $\le 8$  weeks \*
  - $\circ$  Month 3: > 8 to  $\leq$  12 weeks \*
- Excluded from the migraine analysis set
  - < 14 days of eDiary efficacy data in the OP
    

  - < 14 days of eDiary efficacy data in all 3 months of the DBT Phase.

In the categories marked with "\*", subjects must have  $\geq 14$  days of efficacy data (not necessarily consecutive) in the specified month to be evaluable.

#### 6.3.1.2 Descriptive Analyses

The table of values and changes (both absolute and percent) from the OP in the number of migraine days per month in the DBT Phase is provided for the migraine analysis set, and summarizes parameters descriptively as continuous variables (including 2-sided normal 97.5% CIs for mean change) by treatment group and placebo pooled and by pain intensity in each month of the DBT Phase and overall DBT. Pain intensity categories are (1) total (mild, moderate, severe, or not reported) and (2) moderate or severe. The table also presents results by subgroup level for all efficacy subgroups of interest described in Section 4.3.

In the percent change analyses, subjects must have  $\geq 1$  migraine day (i.e., absolute not prorated) of appropriate pain intensity in the OP analysis period to be included.

#### 6.3.1.3 Treatment Group Comparisons

Analyses are based on the migraine analysis set and total pain intensity, unless specified otherwise.

Main Analysis: Migraine Analysis Set

The main analysis of the primary endpoint uses a linear mixed effects model with repeated measures and the following attributes:

- Variables: change from the OP in number of total migraine days per month as the dependent variable; number of total migraine days per month in the OP as a covariate; treatment group, randomization stratum, month (i.e., Months 1 to 3 of the DBT Phase), and the month-bytreatment group interaction as fixed effects.
- Covariance structure for repeated measures accounting for within-subject correlated errors:
   assumed to be homogeneous across treatment groups, and initially specified as unstructured.
   If the model fails to converge or cannot be fit with an unstructured covariance structure, then
   other covariance structures are specified in the following hierarchical order: Toeplitz (which
   has heterogeneous variances and heterogeneous correlations between elements); first-order
   autoregressive with heterogeneous variances; and first-order autoregressive with
   homogeneous variances.
- SE estimation method: Huber-White "sandwich" (refer to the Core SAP).

Note that Protocol Versions 1 to 6 erroneously specify to include subject as a random effect in the model.

The table displays the following model estimates:

- Least-squares mean (LSM) change from OP, SE, and 97.5% CI by month and overall DBT for each treatment group and placebo pooled
- Difference in LSM changes from OP between each zavegepant treatment group and placebo pooled (zavegepanti placebo pooled; *i* = 100 and 200), SE, and 97.5% CI at each month and overall DBT. Results in the overall DBT support the primary objective, results in the last month support secondary objective #2, results in the first month support secondary objective #3, and results in the second month support exploratory objective #1.

See Section 9.3.1 for example SAS code. Model estimates by randomization stratum (yes, no) are presented in the same table, using additional models that exclude randomization stratum as a fixed effect.

The main analyses are repeated for moderate or severe pain intensity to support exploratory objective #1. All variables in the model are the same, except (1) change from the OP in number of moderate or severe migraine days per month is the dependent variable, and (2) number of moderate or severe migraine days per month in the OP is the covariate. The corresponding model table has the same format.

# 6.3.2 Secondary Efficacy Endpoints

## 6.3.2.1 Percentages of Subjects with Reduction in Number of Migraine Days per Month

Analyses are based on the migraine analysis set using eDiary efficacy data dates in the OP and on-DBT efficacy analysis periods (see Section 7.2).

In analyses by months, subjects must (1) achieve the reduction criterion from OP in the number of migraine days per month in the specified month, (2) have  $\geq$  14 days of eDiary efficacy data (not necessarily consecutive) in the specified month, and (3) have  $\geq$  1 migraine day (absolute not prorated) of appropriate pain intensity in the OP analysis period to be classified as responders in the specified month. Otherwise, subjects are classified as failures in the specified month.

In analyses of the overall DBT, subjects must (1) achieve the reduction criterion from OP in the number of migraine days in the overall DBT, and (2) have  $\geq 1$  migraine day (absolute not prorated) of appropriate pain intensity in the OP analysis period to be classified as responders. Otherwise, subjects are classified as failures.

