9.3.1.2 Secondary Efficacy Endpoints

The proportion of subjects with $\geq 50\%$ reduction from the Observation Phase in the number of moderate or severe migraine days per month over the entire DBT Phase (Weeks 1 to 12) will be analyzed using a Cochran-Mantel-Haenszel test stratified by randomization stratum for the migraine analysis set. Missing data are imputed as non-response (i.e., failure). The difference estimate (zavegepant – placebo), SE, 97.5% CI, and p-value will be reported for each dose of zavegepant versus placebo pooled.

The mean change from the Observation Phase in the number of migraine days per month in the last 4 weeks (Weeks 9 to 12) of the DBT Phase will be assessed for the migraine analysis set from the same GLMEM used for the primary efficacy endpoint.

The mean change from the Observation Phase in the number of migraine days per month in the first 4 weeks (Weeks 1 to 4) of the DBT Phase will be assessed for the migraine analysis set from the same GLMEM used for the primary efficacy endpoint.

The mean number of acute migraine-specific medication days per month over the entire DBT Phase (Weeks 1 to 12) will be assessed for the migraine analysis set using a GLMEM that is

similar in structure to that used for the primary efficacy endpoint, except that the number of acute migraine-specific medication days per month is the dependent variable and there is no covariate. Acute migraine-specific medications are triptans and ergotamine.

The mean changes from baseline in MSQ restrictive role function domain score and MIDAS total score at Week 12 will be analyzed for the DBT efficacy analysis set using GLMEMs that will use the identity link function and include the following variables: Week 12 change from baseline in the score as the dependent variable; baseline score as a covariate; and fixed effects for treatment group and randomization stratum. The Week 12 difference estimate (zavegepant – placebo), SE, 97.5% CI, and p-value will be reported for each endpoint and each dose of zavegepant versus placebo pooled.

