#### **Intercurrent Events**

Intercurrent events are those that occur after treatment initiation and either preclude observation of the endpoint or affect its interpretation.

Study drug discontinuation before the time point of interest defining the endpoint is considered an intercurrent event.

• For efficacy objectives assessed with a continuous endpoint during the DBT Phase, study drug discontinuation is handled with a "hypothetical strategy," i.e., the hypothetical scenario is that had subjects not discontinued DB study drug, their efficacy would have been similar to the efficacy of subjects from the same treatment group and randomization stratum who did not discontinue DB study drug. All observed values of the endpoint of interest are excluded after DB study drug discontinuation (see Section 7.2), and statistical methods are used to estimate the treatment effect that would have been seen had the intercurrent event not occurred.

- For efficacy objectives assessed with a binary endpoint during the DBT Phase, DB study drug discontinuation is handled with a "composite strategy," i.e., the occurrence of the intercurrent event is integrated as a component of the endpoint. All observed values of the endpoint of interest are excluded after DB study drug discontinuation (see Section 7.2), and subjects with missing data are considered failures.
- For safety objectives, study drug discontinuation is handled with a "while-on-treatment strategy". All observed values of the endpoint of interest are used on or before study drug discontinuation + 7 days (see Section 7.2 and the Core SAP).
- For outcomes research and other objectives, study drug discontinuation is handled with a "treatment policy strategy", i.e., the occurrence of the intercurrent event is considered irrelevant, such that all observed values of the endpoint of interest are used regardless of study drug discontinuation.

Non-study prophylactic migraine medication use before the time point of interest defining the endpoint is also considered an intercurrent event. For all objectives, this intercurrent event is handled with a treatment policy strategy, such that all observed values of the endpoint of interest are used.

Nonstudy acute migraine-specific medication use before the time point of interest defining the endpoint is also considered an intercurrent event, except for efficacy objectives based on acute migraine-specific medication days or acute migraine medication days.

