# 3.2.2 Secondary Objective Estimands

The estimands corresponding to the secondary objectives are shown in Table 2.

Table 2 Secondary Objective Estimands

Objective 1	Proportion of subjects with ≥ 50% reduction from the OP in the number of moderate or severe migraine days per month over the entire DBT Phase
Efficacy Endpoint	Proportion of subjects with $\geq 50\%$ reduction from OP in number of moderate or severe migraine days per month over the entire DBT Phase (Weeks 1 to 12)
Summary	Percentages by treatment group, and difference in percentages between treatment groups using Mantel-Haenszel risk estimation with stratification by randomization stratum for the migraine analysis set
Intercurrent Events	Study drug discontinuation: composite strategy
	Non-study prophylactic migraine medication use: treatment policy strategy
	Nonstudy acute migraine-specific medication use: composite strategy
	Use of nonstudy other medication to treat headache (migraine or nonmigraine) or aura: treatment policy strategy
Objective 2	Mean reduction from the OP in the number of migraine days per month in the last 4 weeks of the DBT Phase

Efficacy Endpoint	Mean change from OP in the mean number of migraine days per month in the last 4 weeks (Weeks 9 to 12) of the DBT Phase
Summary	Mean change from OP by treatment group using descriptive statistics and linear mixed effects model with repeated measures, and difference between treatment groups from model for the migraine analysis set
Intercurrent Events	Study drug discontinuation: hypothetical strategy
	Non-study prophylactic migraine medication use: treatment policy strategy
	Nonstudy acute migraine-specific medication use: composite strategy
	Use of nonstudy other medication to treat headache (migraine or nonmigraine) or aura: treatment policy strategy
Objective 3	Mean reduction from the OP in the number of migraine days per month in the first 4 weeks of the DBT Phase
Efficacy Endpoint	Mean change from OP in the number of migraine days per month in the first 4 weeks (Weeks 1 to 4) of the DBT Phase
Summary	Mean change from OP by treatment group using descriptive statistics and linear mixed effects model with repeated measures, and difference between treatment groups from model for the migraine analysis set
Intercurrent Events	Study drug discontinuation: hypothetical strategy
	Non-study prophylactic migraine medication use: treatment policy strategy

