## 6.3 Efficacy

Efficacy endpoints are assessed by as-randomized treatment group.

Randomization is stratified using IWRS, but the randomization strata used in analyses are based on actual data. The rationale for using the actual data in analyses is that sites may erroneously report the wrong stratum in IWRS. Hence, treatment group comparisons of continuous efficacy endpoints are *adjusted* by the randomization stratum, whereas treatment group comparisons of binary efficacy endpoints are *stratified* by the randomization stratum (except in subgroup analyses). If there are sparse data within a stratum, then results may be presented unstratified.

In treatment comparisons of binary efficacy endpoints, CIs are based on a normal approximation to the binomial distribution using asymptotic standard error (ASE). Otherwise, CIs for continuous efficacy endpoints are based on the normal distribution. All CIs are 2-sided.

See Sections 7.2 and 7.3 for the definition of efficacy analysis periods and study days.

The by-subject listing of primary and secondary efficacy endpoints is provided for the full analysis set, and includes the reason for exclusion from the migraine analysis set: randomized more than once; not treated with study drug; treated with study drug and < 14 days of eDiary efficacy data in the OP; treated with study drug and < 14 days of eDiary efficacy data in all 3 months of the DBT Phase. Results for continuous endpoints are based on observed data, whereas results for binary endpoints incorporate missing data imputation. Subjects with  $\geq$  14 days of efficacy data (not necessarily consecutive) in the month defining the endpoint are flagged for secondary endpoints based on a single month.

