## 7.2 Analysis Periods

Measurements are slotted into analysis periods based on comparing measurement dates to analysis period reference dates (time is not applicable).

Analysis periods are defined as follows:

- eDiary efficacy endpoints (migraine days, acute migraine-specific medication days, acute migraine medication days)
  - OP: eDiary efficacy data date on or after the OP start date through the OP end date. Note that this is a subset of the pretreatment analysis period.
  - 28-day OP: eDiary efficacy data date on or after the OP start date through the earlier of {OP start date + 27 days; OP end date}. Note that this is a subset of the OP analysis period, and is used only to assess efficacy data issues during the OP as relevant protocol deviations.
  - o On-DBT efficacy:
    - If the DB study drug last date or OL zavegepant start date is not missing: eDiary efficacy data date on or after the DB study drug start date through the earlier of the DB study drug last date and {OL zavegepant start date − 1 day}
    - If the DB study drug last date and OL zavegepant start date are both missing: eDiary efficacy data date on or after the DB study drug start date

This period is used to assess efficacy during the DBT Phase.

- Pretreatment characteristics and safety endpoints \*
  - Pretreatment: This period is abbreviated as "PRETRT" in listings, and is used to derive baseline values.

- o On-DBT safety: This period is abbreviated as "DBT" in safety listings, and is used to assess safety endpoints on DBT for the DBT safety analysis set.
- O Post-DBT pre-OL zavegepant safety: This period is abbreviated as "INT" in safety listings, and is used to assess safety endpoints during the interim period (i.e., post-DBT pre-OL zavegepant) for the interim safety analysis set.
- On-OL zavegepant safety: This period is abbreviated as "OLZAV" in safety listings, and is used to assess safety endpoints for the OL zavegepant safety analysis set.
- On-DB or OL zavegepant safety: This period is used to assess safety endpoints on DB or OL zavegepant treatment for the DB or OL zavegepant safety analysis set.
- On-treatment safety: This period is used to derive analysis visit windows for slotting measurements, and may also be used to assess safety endpoints in a blinded integrated safety report, as needed.
- Follow-up safety: This period is abbreviated as "FU" in safety listings, and is used to assess safety endpoints during follow-up.

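### The Week 1–12 responder rate is labelled composite for study drug discontinuation, but the overall-DBT rule scores early stoppers on their on-drug diary days alone

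*SAP*

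**What the plan says.** SAP 3.2.2, Table 2, Objective 1 gives the strategy for the ≥ 50% reduction in moderate or severe migraine days over Weeks 1 to 12 as "Study drug discontinuation: composite strategy". SAP 3.2 (Intercurrent Events) explains that under this strategy "the occurrence of the intercurrent event is integrated as a component of the endpoint". It carries this out in two steps: values after discontinuation are excluded, and "subjects with missing data are considered failures". Protocol 9.3.1.2 likewise treats missing data as non-response for this endpoint.

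The derivation is in SAP 6.3.2.1. For a single month, a responder must meet the reduction criterion, have at least 14 diary days in that month, and have at least one Observation Phase (OP) migraine day of the relevant intensity. For the full 12 weeks the rule is shorter: "In analyses of the overall DBT, subjects must (1) achieve the reduction criterion from OP in the number of migraine days", plus the same OP condition. It sets no minimum number of diary days and no condition on staying on drug.

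The overall value comes from SAP 6.3.1: 28 times the migraine days, divided by the "total number of eDiary efficacy data days through Month 3" of the on-DBT efficacy period. SAP 7.2 defines that period as "eDiary efficacy data date on or after the DB study drug start date through the earlier of the DB study drug last date", or the day before open-label drug starts if that is earlier. SAP 3.2.3, Table 3, Objective 2 carries the same composite label for the overall-DBT part of that exploratory endpoint.

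**The concern.** A composite strategy makes discontinuation part of the outcome, so a subject who stops drug early should be a failure for the 12-week endpoint. In this plan, discontinuation can act on the result only by making data missing. That works for the monthly rows. In the overall row the value is prorated from whatever on-drug days exist, so discontinuation only shortens the window over which the subject is judged.

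For migraine-set subjects who stop early, the reported figure is therefore a while-on-treatment response under a composite label. SAP 6.3.2.1 names this row as the one that supports secondary objective 1, and SAP 6.3.2.3 carries it into the summary of primary and secondary endpoints. At stake are the reported response rates, their differences and the 97.5% confidence intervals, and what a reader takes them to mean.

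**Working it through.** The documents give no expected rate, power or precision for this endpoint, so there is no planned figure to reproduce. The check traces the rules and then applies them to one subject.

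**Can the overall value be missing?**

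- Denominator of the rate: the migraine analysis set (SAP 6.3.2.1).
- Entry to that set: at least 14 diary days in the OP and in at least one 4-week month of the on-DBT efficacy period (SAP 4.1 and 6.3.1).
- Overall value = 28 × (migraine days) / (diary days), both counted over the on-DBT period through Month 3 (SAP 6.3.1). No minimum applies, although one is set for the OP and for each month.
- The divisor is therefore at least 14 for every subject in the set. The value always exists, and missing-as-failure never acts on this row.

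**Worked subject.** 14 moderate or severe migraine days in a 28-day OP; drug stopped after day 14; 14 on-drug diary days, 3 of them moderate or severe migraine days.

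- OP value: 28 × 14/28 = 14.0 per month.
- Overall DBT value: 28 × 3/14 = 6.0 per month.
- Reduction: 1 − 6/14 = 57%.
- Overall row: responder, with no data for 84 − 14 = 70 of the 84 days.
- Month 2 and Month 3 rows: failure, because there are no diary days in either month.
- Stated composite strategy over 12 weeks: failure.

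**Size.** Let p be the response rate among those who stay on drug, d the share of the migraine set that stops early, and r the share of those early stoppers who meet the criterion on drug.

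- Rate as written: (1 − d)p + d·r.
- Composite rate in the same set: (1 − d)p.
- Excess: d × r.

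The documents give neither d by arm nor r. With assumed values:

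| d | r | Excess (points) |
|---|---|---|
| 5% | 20% | 1.0 |
| 10% | 30% | 3.0 |
| 10% | 40% | 4.0 |

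The effect on the treatment difference is dZ·rZ − dP·rP (Z = zavegepant, P = placebo). It is zero when d and r are equal across arms. With r = 30% in both arms, d of 10% on zavegepant and 5% on placebo gives 3.0 − 1.5 = +1.5 points; the reverse gives −1.5.

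**A second departure, not included in d × r.** Subjects who stop with fewer than 14 diary days in every DBT month are outside the migraine set. They leave the denominator instead of counting as failures.

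**The case against.** The strongest reply is that SAP 3.2 and Protocol 9.3.1.2 already count missing data as failure, and that these general statements govern the overall row. They do show that the composite strategy is intended. But nothing defines an incomplete 12 weeks as missing for the overall value, and SAP 6.3.2.1 lists the conditions for a responder. Following 6.3.2.1 and 6.3.1 literally makes the worked subject a responder. The accurate description is a general rule and a specific rule that conflict and must be reconciled. The Core SAP is not available here, but SAP 6.1.3 sends the reader to SAP 6.3 for missing efficacy data.

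The second reply is that little turns on it, and much of this stands. SAP 5 states that significance will not be evaluated. The Month 1 to 3 rows, which do penalise subjects without enough diary days, appear in the same table as the overall row. The disposition table (SAP 6.2.3.3) and the missing-data table (SAP 6.3.1.1) add context. This reduces the harm, but none of these outputs gives the 12-week composite rate that Table 2 promises.

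A reader might also infer a contradiction from SAP 6.3, where it says "whereas results for binary endpoints incorporate missing data imputation". That sentence describes a by-subject listing for the full analysis set. The listing includes subjects outside the migraine set, whose overall value can be missing, so imputation can act there. It is not evidence for this point.

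**Conclusion.** The mismatch is real. For secondary objective 1 and the overall-DBT part of exploratory objective 2, the rule as written does not estimate the composite quantity that the estimand tables state. Migraine-set subjects who stop early are judged on their on-drug days alone.

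Within the migraine set, each arm's rate exceeds the composite rate by d × r, or 1 to 4 points for assumed d of 5–10% and r of 20–40%. These are illustrations, not estimates.

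Three stronger readings are not supported:

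- *The rule favours zavegepant.* The sign depends on which arm has the larger d × r, and the documents do not say.
- *The planned OLE intake caps the error.* Protocol 5.1 expects about 1200 of 1440 subjects to enter the OLE, and Protocol 4.3.3 bars early stoppers from it. But 1200 is an overall planning estimate that does not limit d in any one arm, and r is unknown.
- *The rate is purely while-on-treatment.* The earliest stoppers drop out of the set altogether.

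No test decision is affected. The plan should be corrected so that the label and the number agree.

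**What to change.** **Preferred.** In SAP 6.3.2.1, add to the overall-DBT rule that a subject who discontinued DB study drug before the end of the DBT Phase is a failure. The sponsor should define the flag from two inputs the SAP already has: the DB Subject Status completion response (SAP 6.2.3.3) and the DB study drug last date (SAP 7.1). The definition needs:

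- a cut-off tied to the efficacy Month 3 interval (study days 57 to 84, SAP 6.3.1) and to visit timing;
- a rule for subjects marked as completers whose dosing records are incomplete, because the last date is only the latest recorded dosing date.

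Keep the present on-drug rule as a supplementary result labelled while-on-treatment.

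**Alternative.** Keep the present rule as the main result. Relabel only the overall-DBT rows in Table 2 Objective 1 and Table 3 Objective 2 as while-on-treatment. Add a matching exception in SAP 3.2 that leaves the monthly rows composite, and report the composite version alongside. Relabelling the whole binary-endpoint bullet in SAP 3.2 would wrongly change the monthly rows.

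Under either option, state that stoppers with fewer than 14 diary days in every DBT month are outside the denominator.

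**Cost.** One SAP paragraph and one derived flag, or two table entries, one exception and one added result. No new data are needed. Under the preferred option the main rates fall by d × r in each arm. Any version added after unblinding should be labelled post hoc.
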